Appendix I	
Cook manufacturing and labeling device information	

Background

Many studies have reported on the safety and efficacy of endovascular aneurysm repair over the past eight years. As endovascular grafting has evolved, its applicability has increased substantially. However, it remains difficult to establish defined criteria for patient selection, largely due to the rapidly changing technology available. The device to be studied in this proposal is the product of a world wide collaborative effort to provide an endoluminal prosthesis that is easily and safely deployed to provide complete and durable aneurysm exclusion. All non-clinical testing was performed in the United States was performed to comply with the Good Laboratory Practice regulations.

The device to be tested has been in use in Perth Australia since 1994^{1,2}, having evolved in parallel with devices in Sweden³⁻⁶, England⁷, and the United States^{8,9}. The one-time aorto-uniiliac device is now a modular bifurcated system. The delivery device has decreased substantially in size while providing an increased degree of flexibility. The proximal aortic attachment site more closely resembles an anastomotic equivalent. The device, throughout its evolution, has been placed in over 500 patients, however experience with the bifurcated version of this graft is limited to 108 patients². Several recent modifications, particularly with regard to delivery mechanisms and the modular configurations have been made in an effort to broaden the selection criteria and prevent some of the long-term complications encountered with other types of endovascular grafts.

Of the 108 patients receiving bifurcated endografts in Perth, successful deployment was achieved in 103 patients (95 percent) with a median follow-up period of 18 months. There were 9 cases (8.3 percent) of primary endoleak (defined as an endoleak detected on CT scanning prior to hospital discharge). However, 15 endoleaks (13.8 percent) were noted at the six-week follow-up evaluation, inclusive of the original 8.3 percent. Of this group, 7 patients (47 percent) were successfully treated with adjuvant endovascular procedures, 4 (26 percent) sealed spontaneously, 2 patients died of unrelated causes, and 2 endoleaks remain under close observation. Three patients (2.7 percent) presented with limb occlusion during the follow-up period. Of the original 108 patients, 91 are still alive. Twelve deaths were secondary to unrelated causes, and the causes of two deaths are unknown. Two perioperative deaths occurred attributed to the procedure, and one patient died of mesenteric ischemia following endoluminal repair². Overall, the results compare favorably with historical surgical controls.

Experience with regard to the use of endografts at the University of Rochester includes participation in the Vanguard trial run by Boston Scientific – Meadox. This involved the placement of both modular bifurcated devices and tube grafts in 20 patients. We are currently participating in the Talent trial, and a number of homemade stent-grafts have been placed on a compassionate basis.

1.0 Purpose

The purpose of this study is to assess the role of abdominal aneurysm exclusion using an endovascular prosthesis.

1.1.0 Objectives

- 1) To assess the safety and efficacy of an endovascular prosthesis as a means of preventing aneurysm growth and rupture in high-risk patients.
- 2) To measure the physiologic effects and outcomes of endovascular aneurysm repair.
- 3) Establish selection criteria, improve device design, operative technique and follow-up procedures for patients undergoing endovascular aneurysm repair.

1.2.0 Duration of Investigation

Duration of the investigation will include a twenty-four month follow-up period, however, the patients will be followed for their lifetime with regard to the continued assessment of endovascular aneurysm exclusion and risk for rupture.

2.0 Characteristics of the Research Population

- 1) Number of subjects. A total of 300 high risk patients will be enrolled in this study. The study will be conducted at the Cleveland Clinic Foundation. Enrollment will be on a rolling basis.
- 2) Gender of subjects. Gender is not an issue in this study. Enrollment will occur on a rolling basis regardless of gender.
- 3) Age of subjects. Subjects must be over 18 years of age. There is no maximum age however, patients must have an approximated life expectancy greater than 2 years.
- 4) Racial and ethnic origin. Racial and ethnic origin is not an issue in this study.
- 5) Inclusion criteria

General:

- a) the aneurysm is 5 cm or larger, or with a high risk of rupture due to its shape, history of growth, symptoms, or the presence of a large (>3.5 cm) iliac aneurysm
- b) anticipated mortality greater than 10 percent with conventional surgery*
- c) life expectancy greater than 2 years
- d) suitable arterial anatomy
- e) absence of systemic disease or allergy that precludes an endovascular repair
- f) capable of giving informed consent and willingness to comply with the follow-up schedule

* The risk of death following conventional operation (called “anesthetic risk”, although this is more closely related to the effects of surgery) will be determined primarily by the extent of co-morbid conditions, particularly cardiopulmonary disease. Clinical assessment will be determined in concert with medical and anesthesiology consultants when needed. Many factors weigh into the determination of operative risks. There are a wide variety of methods for attempting to quantify the relative effects of each risk factor however this has been done without reproducibility. In addition to the anesthetic risk, this analysis takes into account other risk factors for open surgical repair, such as retroperitoneal fibrosis, inflammatory bowel disease, prior radiation therapy, intestinal fistulae, and prior surgical procedures, all of which may complicate conventional surgical repair.

Anatomic:

- a) proximal neck > 10mm in length, \leq 32mm in diameter, and angulated no more than 80 degrees relative to the long axis of the aneurysm
- b) iliac artery diameter > 7mm (following balloon angioplasty or stenting if necessary)
- c) no signs that the inferior mesenteric artery is indispensable. These include angiographic visualization of a large IMA, filling of SMA via collaterals, or significant stenoses of the celiac or SMA.
- d) iliac artery angulation < 90 degrees. In the presence of significant calcifications, the angle should be less than 60 degrees.
- e) for a straight aorto-aortic prosthesis, the distal neck (normal aorta between the aneurysm and iliac bifurcation) must be greater than 15mm in length, and less than 26mm in diameter.
- f) for a bifurcated aorto-biiliac prosthesis, the iliac implantation sites must be less than 2 cm in diameter and greater than 2 cm in length.

6) Exclusion criteria

- a) pregnancy
- b) history of anaphylactic reaction to contrast material with an inability to properly prophylax the patient appropriately
- c) allergy to stainless steel or polyester
- d) unwilling to comply with the follow-up schedule
- e) serious or systemic groin infection
- f) coagulopathy, other than coumadin therapy
- g) inability to give informed consent

7) Vulnerable subjects. Subjects must be older than 18 years of age and capable of giving informed consent

3.0 Methods and Procedures

3.1.0 Study Design

This study will be a prospective, non-randomized evaluation of endovascular aneurysm repair in high-risk patients.

Patients will be selected based upon the following criteria:

- Patients will be considered high risk if they meet any of the “General Inclusion Criteria”
- Patients will be considered anatomically suitable if they fulfill all of the appropriate “Anatomic Inclusion Criteria”

Patients must meet both the general and anatomic criteria to be enrolled in the study. General inclusion criteria will be assessed during the initial patient evaluation by conducting a history and physical examination. Anatomic criteria will be assessed using a variety of imaging techniques that are routinely performed during the evaluation of abdominal aortic aneurysms (see appendix A: Imaging Techniques Summary). The choice of axial imaging technique will be left up to the referral physician provided that the imaging protocol utilized is adequate for complete preoperative planning as defined in Appendix 1. Angiography and intravascular ultrasound will be performed selectively as is currently done prior to infrarenal abdominal aneurysm repair.

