4.3.0 Potential benefits to the subjects and alternative treatments

Although this procedure is being performed world wide for both high and low risk patients, the benefits offered to high risk patients are straight forward. The best method to evaluate these benefits is to compare the potential alternative treatment modalities to that of endovascular repair.

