4.3.1 Observation

A patient who is not treated is at risk for aneurysm rupture at an overall rate that depends on the aneurysm's size and the patient's longevity. All patients eligible for inclusion in this study have a high risk of rupture, based primarily on aneurysm size. Once the aneurysm has ruptured, it is usually too late to consider treatment in this patient sub-group as most will die.

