4.3.2 Conventional surgery

Conventional repair of abdominal aortic aneurysms is highly effective at preventing aneurysm rupture. However, it is associated with a significant degree of cardiopulmonary complications as a result of a prolonged abdominal operation, significant blood loss and aortic cross clamping. Low risk patients are defined as such because they have enough cardiopulmonary reserve to withstand traditional therapy. Despite the potential for the development of

bowel obstructions, graft infections, occlusions and paraanastomotic aneurysms, the long-term risks of open surgical repair are small. The initial physiologic insult are significant but difficult to quantify. A prospective multi-center review involving 666 aneurysm patients calculated a 15 percent risk of cardiac complications, 8.4 percent risk of pulmonary issues, and 6 percent risk of postoperative renal dysfunction¹³. However, these risks were noted to be both surgeon and institution dependent¹⁴.

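### The high-risk test in Section 3.1.0 is met by every otherwise eligible patient, so as written it does not ensure the high-risk population the protocol names

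*Combined protocol and SAP*

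**What the plan says.** Section 3.1.0 introduces two selection bullets. The first reads "Patients will be considered high risk if they meet any of the" general inclusion criteria. The second calls a patient anatomically suitable only if all of the appropriate anatomic criteria are fulfilled. The text then adds: "Patients must meet both the general and anatomic criteria to be enrolled in the study".

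The general list appears in Section 2.0, item 5, and again in Section 3.1.1, where the heading describes it as the criteria for high-risk patients. In short form, its six items are:

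- (a) aneurysm size or other features of high rupture risk
- (b) expected mortality above 10 percent with open repair
- (c) life expectancy above 2 years
- (d) suitable arterial anatomy
- (e) no systemic disease or allergy that rules out endovascular repair
- (f) able to consent and willing to be followed

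The exclusions in Section 2.0, item 6 (repeated in 3.1.2) include "unwilling to comply with the follow-up schedule" and "inability to give informed consent".

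On the intended population, Section 2.0, item 1 states: "A total of 300 high risk patients will be enrolled in this study". Objective 1 in Section 1.1.0 is likewise confined to high-risk patients. Section 4.3.1 says: "All patients eligible for inclusion in this study have a high risk of rupture, based primarily on aneurysm size".

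**The concern.** Only (b) concerns operative risk and only (a) concerns the aneurysm. The other four items are conditions for taking part and say nothing about risk. A rule that confers the high-risk label on any one of the six can be satisfied by an item that has nothing to do with risk.

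The consequence is a contradiction inside the protocol. Section 4.3.2 says: "Low risk patients are defined as such because they have enough cardiopulmonary reserve to withstand traditional therapy". A patient of that kind who has suitable anatomy and consents is low risk under Section 4.3.2 and high risk under Section 3.1.0.

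The study is non-randomized, so what its results mean depends on who was enrolled. Section 4.3.0 argues the benefit for high-risk patients specifically and adds: "The best method to evaluate these benefits is to compare the potential alternative treatment modalities to that of endovascular repair". That argument does not carry over to patients who could tolerate open repair, for whom Section 4.3.2 calls the long-term risks of surgery small and Section 4.3.3 voices concern about long-term endovascular results. If staff followed Section 3.1.0 literally, such patients could enter and dilute the safety and efficacy results. A reader could not tell from the rule whether (a) and (b) had been applied.

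**Working it through.** The documents give no hypothesis, power or margin for the 300 patients, so there is no plan figure to reproduce. The check is one of logic.

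**Step 1: which general criteria are met automatically.**

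- Passing the anatomic criteria (Section 3.1.3) implies (d).
- Not being excluded for refusing follow-up or for inability to consent (Section 3.1.2, d and g) implies (f).

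An anatomically suitable, non-excluded patient therefore already meets two of the six, and one is enough under *any*.

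**Step 2: count the patterns.** Six criteria, each met or unmet, give 2^6 = 64 patterns.

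| Held as met | Patterns | Pass under *any* | Of these, (b) unmet | Pass under *all* |
|---|---|---|---|---|
| none | 64 | 63 | not needed here | 1 |
| (d), (f) | 2^4 = 16 | 16 | 8 | 1 |
| (c), (d), (f) | 2^3 = 8 | 8 | 4 | 1 |
| (c), (d), (e), (f) | 2^2 = 4 | 4 | 2 | 1 |

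The third row holds (c) fixed because Section 2.0, item 3 separately makes life expectancy mandatory. The fourth also fixes (e), which the exclusions cover in part. Whichever row is preferred, once (d) and (f) are met *any* rejects nothing, half the admitted patterns lack (b), and *all* admits none without (b). These counts describe the rule and are not estimates of patient numbers.

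**Step 3: does other text repair the rule?**

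- The sentence requiring both sets of criteria does not say how many general criteria are needed, and it follows a bullet that has just said *any*.
- Section 5.1.0 refers to meeting the clinical and anatomic criteria, again without a number.
- Sections 2.0 and 3.1.1 list the six items without *any* or *all*.
- Nothing states which section prevails.

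**Step 4: illustration of dilution, on assumed figures.** The documents give no open-repair mortality by risk group. Let H be open-repair mortality in patients meeting (b), L that in low-risk patients, and p the low-risk share. Expected open-repair mortality in the cohort falls by p × (H − L). With p = 0.10:

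- H = 12%, L = 5%: 0.10 × 7 = 0.7 points, or 300 × 0.007 = 2.1 deaths
- H = 20%, L = 2%: 0.10 × 18 = 1.8 points, or 300 × 0.018 = 5.4 deaths
- H just above the protocol's threshold, taken as 10%, L = 5%: 0.10 × 5 = 0.5 points, or 300 × 0.005 = 1.5 deaths

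These are the deaths expected had the same patients had open repair. They show how far a high-risk benchmark would misdescribe a mixed cohort. No planned test depends on them.

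**The case against.** The strongest reply is that the *any* bullet only assigns a label, and that enrolment is governed by the later sentence requiring both sets of criteria. To meet a list of criteria ordinarily means to meet each item, Sections 2.0 and 3.1.1 present the six as plain inclusion criteria, and life expectancy is stated elsewhere as mandatory. The literal reading would not even require a large or threatening aneurysm, which Section 4.3.1 rules out. This is a single-centre study in which the investigator reviews history, examination and imaging before consent (Section 5.2.0), so low-risk enrolment is speculative.

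Much of this is fair. A cumulative intent is likely, and nothing shows that low-risk patients will be enrolled. Section 4.3.1 supports (a) rather than (b). Sections 4.3.0 and 4.3.2 are background discussion and are neither an analysis plan nor an eligibility definition. The mortality illustration rests wholly on assumptions. Section 3.2.2 records cardiac, renal and pulmonary disease before the procedure, and the content of the Appendix E form is not available to check, so some evidence on risk status may be collected.

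The reply does not remove the defect. The paragraph introduces its bullets as the basis for selecting patients, and it sets *any* beside *all*, which makes it hard to read one as the other. A reader has to infer the intended rule from other sections. Section 2.0 also concedes that operative risk has not been quantified reproducibly, so (b) rests on judgement, which makes it more important to say plainly whether it is required.

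**Conclusion.** The concern holds. As written, the high-risk test in Section 3.1.0 excludes no otherwise eligible patient and requires neither (a) nor (b): 16 of 16 patterns pass, 8 of them without (b), against 1 and 0 if all six criteria were required. This conclusion needs only that (d) follows from the anatomic criteria or that (f) follows from the exclusions; either one is enough. It is most probably a drafting conflict, but it sits in the selection rule and leaves the study population undefined on paper, so it needs correcting. The claim is that the rule does not ensure a high-risk cohort; it is not that the cohort will be low risk. On the assumed mortalities, each 10 percent of low-risk patients would lower the cohort's expected open-repair mortality by roughly 0.5 to 1.8 percentage points. The verdict does not depend on that range.

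**What to change.** Reconcile Section 3.1.0 with Sections 2.0, 3.1.1 and 4.3.1 in one sentence that states which general criteria are each required and which define high risk. Replacing *any* with *all* would match the population the protocol names; at a minimum the text should say whether (a) and (b) are mandatory. The choice rests with the sponsor and the investigator.

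Optionally, if the Appendix E case report form does not already do so, record before the procedure that (b) was met and the main reason, so that the enrolled population can be verified.

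The cost is a change to one sentence and at most one tick-box with a reason. If the criteria were always meant to be cumulative, no intended patient is lost. If they were not, some low-risk referrals would no longer qualify, which is consistent with the stated objective.

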3.1.1 Inclusion Criteria – High Risk Patients

- a) the aneurysm is 5 cm or larger, or with a high risk of rupture due to its shape, history of growth, symptoms, or the presence of a large (>3.5 cm) iliac aneurysm
- b) anticipated mortality greater than 10 percent with conventional surgery*
- c) life expectancy greater than 2 years
- d) suitable arterial anatomy
- e) absence of systemic disease or allergy that precludes an endovascular repair
- f) capable of giving informed consent and willingness to comply with the follow-up schedule

3.1.2 Exclusion Criteria

- a) pregnancy
- b) history of anaphylactic reaction to contrast material with an inability to properly prophylax the patient appropriately
- c) allergy to stainless steel or polyester
- d) unwilling to comply with the follow-up schedule
- e) serious or systemic groin infection
- f) coagulopathy, other than coumadin therapy
- g) inability to give informed consent

3.1.3 *Anatomic Criteria*

- a) proximal neck > 10mm in length, <= 32mm in diameter, and angulated no more than 80 degrees relative to the long axis of the aneurysm
- b) iliac artery diameter > 7mm (following balloon angioplasty or stenting if necessary) and < 20mm
- c) no signs that the inferior mesenteric artery is indispensable. These include angiographic visualization of a large IMA, filling of SMA via collaterals, or significant stenoses of the celiac or SMA.
- d) iliac artery angulation < 90 degrees. In the presence of significant calcifications, the angle should be less than 60 degrees.
- e) for a straight aorto-aortic prosthesis, the distal neck (normal aorta between the aneurysm and iliac bifurcation) must be greater than 15mm in length, and less than 26mm in diameter.
- f) for a bifurcated aorto-biiliac prosthesis, the iliac implantation sites must be less than 2 cm in diameter and greater than 2 cm in length.

3.1.4 *Stent-graft sizing*

Grafts are currently custom made for each patient based on the findings from preoperative radiologic studies, including computerized tomography, magnetic resonance imaging, and conventional angiography. See appendix A for a detailed protocol of the imaging studies to be obtained.

3.1.4.1 **Stent-graft diameter**

The diameter of the graft is intended to be 10 to 15 percent (usually 3-4 mm) larger than the proximal implantation site (see appendix B). The attachment site for distal implantation is oversized by 5 to 10 percent (see appendix C). The assumption being that a small amount of graft redundancy would be inconsequential, whereas, as small deficiency in the diameter of the graft would result in either endoleakage or graft migration.

Straight grafts (aorto-aortic) are of uniform diameter. The larger of the two implantation sites determines the diameter of the graft. Aorto-iliac grafts (uni-iliac and bifurcated devices) have different proximal and distal diameters. Additionally, bifurcated devices may have differently sized segments at the ends of their right and left limbs.

Determination of proximal graft diameter depends primarily on a measurement of the aneurysm neck from axial reconstructions of CT data. When the neck of the aneurysm appears to have an elliptical section on trans-axial images, the true profile is assumed to be circular, and the true diameter is the diameter of the

narrowest part of the ellipse. The elliptical appearance is thus reflective of the aortic tortuosity and obliquity of the slice.

3.1.4.2 Stent-graft Length

Given the tension of the graft at the time of distal stent implantation, it is assumed that the graft will take the shortest path available from the renal arteries to the aortic bifurcation. For straight aorto-aortic grafts, the prosthesis corresponds to the length of the infrarenal aorta. For aorto-iliac grafts, the distal implantation site is the common iliac artery; the graft length is such that the end of the graft is at least 2 cm from the aortic bifurcation while remaining 1 cm above the common iliac bifurcation. The primary imaging modality used to determine the length of the graft will vary depending on the tortuosity of the aorta and the availability of multiplanar reconstructions, surfaced shaded displays, and other representations of spiral CT data or angiographic images. Trans-axial CT images can be used for length assessment only when the aorta is relatively straight, the intervals between the slices small, and in the absence of good quality, properly calibrated angiographic images.

3.1.5 Device Manufacture and Sterilization

Cook Incorporated will manufacture the devices. I have no detailed information on the methods of manufacture. However, many features of the device are similar to the previous devices utilized at the University of San Francisco. Having already performed several aneurysm repairs with the Perth device Australia and Malmo, Sweden, I am very familiar with the most recent version. However, with regard to manufacturing details, I can do no better than to refer you to the most recent publication of the largest series of patients undergoing aneurysm repair with this device², included as appendix D. The device will not be sold. There will be no charge to patients for the use of the device.

Devices shipped under the Investigational Device Exemption are intended to be used for clinical studies in which waste will be controlled or the amount of waste expected to enter the environment may reasonably be expected to be nontoxic.

